8.2 Pharmacodynamic assessment

This section does not apply to this study.

8.3 Safety assessment

The safety of ABSK061 will be evaluated during the trial by recording adverse events, laboratory tests, vital signs, electrocardiograms, and physical examinations. During the study, the symptoms and signs of the participants after administration should be closely observed. Adverse events or adverse drug reactions should be handled promptly and effectively to ensure

the safety and rights and interests of participants. The type, symptoms, time of onset, degree (or grade), symptomatic treatment and outcome of adverse events should be recorded, and then the adverse events should be analyzed, assessed and statistically analyzed.

8.3.1 Demographic and Disease History

Demographic and medical history information will be collected for all participants at the times indicated in Table 4 Part I study plan, Table 5 Part II study plan, and Table 6 Part III study plan. Demographic information will include participant gender, ethnicity, and date of birth.

Participants will be carefully asked about past medical history and treatment information, food allergy, drug allergy, concomitant diseases and treatments, and smoking and alcohol consumption during the screening period. Past medical history and concomitant diseases should record the disease name, time of onset and drug use in detail; history of drug and food allergy should document drug or food name and allergy symptoms.

8.3.2 Vital signs

For each participant, vital signs including ear temperature, sitting blood pressure, respiratory rate, and pulse rate will be measured according to Table 4 Part I study plan, Table 5 Part II study plan, and Table 6 Part III study plan. Vital signs are recommended after the participant has rested quietly for at least 5 minutes. Vital signs should be performed prior to PK blood sampling or at least 20 min apart after PK blood sampling. Additional vital sign testing may be added during each study at the discretion of the investigator. If the vital signs test results at screening are not within the normal range, they may be repeated once, and if they are still not within the normal range, the screening fails; participants who have been assigned a randomization number/enrollment number may be retested once if the vital signs test results before the first dose on D1 are not within the normal range, or drop out if they remain within the normal range and are judged by the investigator to be clinically significant.

Normal Vital Sign Range:

- $35.9 \,^{\circ}\text{C} \le \text{ear temperature} \le 37.5 \,^{\circ}\text{C}$
- 90 mmHg \leq systolic blood pressure < 140 mmHg, 60 mmHg \leq diastolic blood pressure < 90 mmHg
 - 12 beats/min ≤ respiratory rate ≤ 22 beats/min
 - 55 beats/min ≤ pulse rate ≤ 100 beats/min

Additional vital sign assessments may be added at scheduled visit timepoints as clinically indicated. Additional orthostatic vital sign assessments should be performed for any AE associated with dizziness, an AE in which differences in body posture may cause symptoms. If an upright measurement is required, the participant should stand for at least 3 minutes first. If the participant feels unable to stand, only supine vital signs will be recorded.

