- 2. Study period: dosing on Day 1 (D1) and washout from D1 to D3 were included. Participants should be admitted to the clinical study ward of the study site on the day prior to dosing (i.e., D-1), eat uniformly, and undergo relevant visit examinations. Participants cannot leave the clinical study ward of the study site during the trial.
- 3. Participants should be contacted by telephone follow-up on D8 (+ 3 days) 7 days after administration of ABSK061 and information on adverse events and concomitant medications should be collected.
 - 4. Early withdrawal applies to participants who have received ABSK061 and will no longer be followed for safety.
 - 5. Demographic data will include gender, ethnicity, and date of birth of the participant.
- 6. Medical history inquiry: including past medical history and treatment history, smoking history, alcohol consumption history, drug allergy history, food allergy history, concomitant diseases and treatment. The inquiries are detailed in Protocol 8.3.1 Demographics and Disease History.
- 7. Vital signs included ear temperature, sitting blood pressure, respiratory rate, and pulse rate. Vital signs are recommended after the participant has rested quietly for at least 5 minutes. Vital signs should be measured at 1 hour (± 1 hour) pre-dose, 2 hours (± 1 hour) post-dose, 6 hours (± 1 hour) post-dose, 24 hours (± 1 hour) post-dose, 48 hours (± 1 hour) post-dose, and at the Early Withdrawal Visit. Vital signs should be performed prior to PK blood sampling or at least 20 min apart after PK blood sampling. Additional vital sign testing may be added during each study at the discretion of the investigator. If the vital signs test results at screening are not within the normal range, they may be repeated once, and if they are still not within the normal range, the screening fails; participants who have been assigned a random number may be retested once if their vital signs test results are not within the normal range prior to the first dose on D1, or drop out if they are still outside the normal range and judged by the investigator to be clinically significant.

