- 9. Vital signs included ear temperature, sitting blood pressure, respiratory rate, and pulse rate. Vital signs are recommended after the participant has rested quietly for at least 5 minutes. Vital signs in each period should be measured at 1 hour (± 1 hour) pre-dose, 2 hours (± 1 hour) post-dose, 6 hours (± 1 hour) post-dose, 24 hours (± 1 hour) post-dose, 48 hours (± 1 hour) post-dose, and at the Early Withdrawal Visit. Vital signs should be measured before or after at least a 20-minute interval after PK blood sampling. Additional vital sign testing may be added during each study at the discretion of the investigator. If the vital signs test results at screening are not within the normal range, they may be repeated once, and if they are still not within the normal range, the screening fails; participants who have been assigned a randomization number may be retested once if the vital signs test results prior to the first dose on D1 of Cycle 1 are not within the normal range or drop out if they are still not within the normal range and are judged by the investigator to be clinically significant.
- 10. Physical examination: a complete physical examination is required at screening or baseline, and only a general physical examination will be performed during subsequent studies. A complete physical examination included mucocutaneous, lymph nodes, head, neck, chest, abdomen, spine, extremities, and nervous system. General physical examination, which may include head and neck, chest and abdomen, will be determined by the investigator as clinically indicated.

- 11. Height and weight: collected at Screening or Baseline only. Investigators may perform more frequent tests if clinically indicated.
- 12. Hematology: including red blood cell count (RBC), hemoglobin (HGB), hematocrit (HCT) and total platelet count (PLT), white blood cell count (WBC) with differential and proportion (including neutrophil percentage and absolute neutrophil percentage, lymphocyte percentage and absolute lymphocyte count, monocyte percentage and absolute monocyte count, eosinophil percentage and absolute basophil percentage). If hematology at screening is performed within 7 days prior to the first dose, hematology will not be performed separately at baseline on D-1.

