- 19) Those with a history of needle sickness, blood sickness or intolerance to venipuncture, or difficulty in blood collection;
- 20) Abnormal physical examination, hematology, blood chemistry, coagulation function, urinalysis, 12-lead electrocardiogram, chest X-ray (anteroposterior), abdominal B-ultrasound, ophthalmic examination and judged by the investigator to be clinically

significant;

- 21) Vital signs outside the normal range, and the retest is still outside the normal range.
- 22) Abnormal serum hepatitis B surface antigen (HBsAg), hepatitis C virus (HCV) antibody, human immunodeficiency virus (HIV) antibody, treponema pallidum antibody test and judged by the investigator to be clinically significant;
- 23) Personnel involved in the design or implementation of this study project and their immediate family members (e.g., employees of Shanghai Hezhui Biopharmaceutical Technology Co., Ltd., CRO employees, and employees of the study site);
- 24) Any other factor that, in the opinion of the investigator, is not suitable for enrollment, may affect the compliance of the participant with the protocol, affect the interpretation of the study results, or increase the participant's safety risk, or the participant withdraws from the trial for his/her own reasons.

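### Protocol section 8.3.2 states the Day 1 pre-dose vital-sign drop-out condition in the opposite direction from the footnotes to Tables 4, 5 and 6

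*Protocol*

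**What the plan says.** Section 8.3.2 covers all three Parts. It applies the rule to participants who already hold a randomization or enrollment number. The trigger for a second measurement is that they "may be retested once if the vital signs test results before the first dose on D1 are not within the normal range". The condition for leaving the study then reads: "or drop out if they remain within the normal range and are judged by the investigator to be clinically significant". The numeric normal limits for ear temperature, blood pressure, respiratory rate and pulse rate follow directly below.

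The schedule footnotes address the same moment:

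- Table 4 footnote 7 (Part I) and Table 5 footnote 7 (Part II): "or drop out if they are still outside the normal range and judged by the investigator to be clinically significant".
- Table 6 footnote 9 (Part III, Day 1 of Cycle 1): "or drop out if they are still not within the normal range and are judged by the investigator to be clinically significant".

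Two neighbouring rules bear on the reading. For screening results, section 8.3.2 itself says that "they may be repeated once, and if they are still not within the normal range, the screening fails". Exclusion criterion 21, in the synopsis and in section 5.2.2, excludes participants with "Vital signs outside the normal range, and the retest is still outside the normal range". It makes no reference to clinical significance.

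**The concern.** The rule decides whether a healthy participant with an abnormal reading on the morning of dosing goes on to receive the drug. Section 8.3.2 and the footnotes attach drop-out to opposite retest results, and both are current text. The footnotes refer to a normal range without giving numbers, so staff applying any footnote must turn to section 8.3.2 for the limits, and there they meet the reversed sentence.

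At stake is an ambiguous instruction at a point that is hard to undo. Section 7.2 replaces a participant who is never dosed, within the same sequence, but does not allow a dosed participant to be replaced. A site could also be recorded as deviating from one passage while complying with another.

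**Working it through.** No figure is involved, so the check is a comparison of texts.

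**Step 1: direction of the Day 1 drop-out condition, by place.**

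| Place | Retest result that leads to drop-out | Clinical significance also required |
|---|---|---|
| Section 8.3.2 (all Parts) | within range | yes |
| Table 4 footnote 7 (Part I) | out of range | yes |
| Table 5 footnote 7 (Part II) | out of range | yes |
| Table 6 footnote 9 (Part III) | out of range | yes |
| Exclusion criterion 21 (eligibility) | out of range | no |

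The three footnotes agree with one another. Section 8.3.2 is the one that differs in direction.

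**Step 2: internal consistency of section 8.3.2.** The retest is offered only when the first result is out of range. A result that was out of range cannot then remain in range, so the drop-out condition does not fit its own trigger. The screening clause in the same sentence fails a participant whose repeat is still out of range, which is the other direction again.

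**Step 3: each possible retest outcome under each text, read literally.**

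| Retest outcome | Section 8.3.2 | Table footnotes | Exclusion criterion 21 |
|---|---|---|---|
| In range, judged significant | drop out | no drop-out stated | not excluded |
| In range, not significant | no drop-out stated | no drop-out stated | not excluded |
| Out of range, judged significant | no drop-out stated | drop out | excluded |
| Out of range, not significant | no drop-out stated | no drop-out stated | excluded |

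Section 8.3.2 and the footnotes disagree in the first and third rows. The footnotes and exclusion criterion 21 disagree in the fourth. That second difference exists whatever is done about section 8.3.2. Whether it operates on Day 1 is not settled by the text, because Tables 4 to 6 mark the eligibility check only at screening and Day -1.

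**Step 4: who can be affected.** All 18 + 12 + 12 = 42 planned participants are due a pre-dose measurement on Day 1. Only those whose first Day 1 result is out of range reach the disputed clause. The protocol gives no figure from which that number could be estimated.

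**The case against.** The strongest reply is that the slip exposes itself. The sentence makes sense only with a negation, the screening half of the same sentence has one, three footnotes agree, and the English text shows other signs of rough translation. An experienced investigator would probably notice. This stands as an account of the likely cause, although it cannot be proved without the source-language text. It limits the practical risk but does not make the written rule correct.

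Several stronger readings are tempting, and the protocol does not support them:

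- *That section 8.3.2 removes anyone whose retest is in range.* It also requires a judgement of clinical significance, so an ordinary in-range retest triggers nothing.
- *That an out-of-range participant is left with no rule at all.* The footnotes cover the case on Day 1. Exclusion criteria 21 and 24 address it as eligibility rules, and section 7.11 lets the investigator withdraw a participant on clinical grounds.
- *That section 8.3.2 overrides the tables.* It refers to Tables 4 to 6 for the measurements, and section 7.1 refers to them for specific procedures. Neither statement settles which text governs drop-out, and no order of precedence is stated.
- *That this is the last eligibility check before dosing.* The tables place the eligibility check at screening and Day -1, and pre-dose ECGs are also taken on Day 1.
- *That the PK or safety results would be distorted.* The analysis sets in section 9.2 depend on dosing and samples, and an undosed participant is replaced in the same sequence. No effect on any estimate has been shown.

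**Conclusion.** The contradiction is real. Section 8.3.2 gives the Day 1 pre-dose drop-out condition in the reverse direction from all three schedule footnotes, and it is inconsistent with its own trigger and screening clause. The conclusion rests on the current English wording alone. A lost negation is the probable cause, but that is an inference.

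The size is modest. One passage stands against three, and the difference matters only for participants with an out-of-range first reading on Day 1, whose number is unknown. It merits correction because it is a participant-level safety rule printed beside the only numeric limits, not because any planned analysis is shown to be affected. A reader might infer that all 42 participants are exposed to the error; all are measured, but only those with an out-of-range first reading come under the clause.

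**What to change.** Reconcile section 8.3.2 with Table 4 footnote 7, Table 5 footnote 7 and Table 6 footnote 9, so that one identical rule, tied to the limits listed in section 8.3.2, appears in all four places.

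In the same edit, reconcile these passages with exclusion criterion 21 in the synopsis and section 5.2.2. State whether clinical significance is part of the condition, and whether that criterion applies on Day 1 or only at the marked eligibility checks.

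Which rule applies is for the sponsor to decide; none is proposed here. The cost is a sentence in section 8.3.2, plus matching wording elsewhere where needed, in a protocol amendment or clarification letter. No sample size, schedule or analysis changes.

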8.3.3 Physical examination, height and weight

The physical examination, which includes a complete physical examination at screening and a general physical examination during the subsequent study, will be performed at the times indicated in Table 4 Part I study plan, Table 5 Part II study plan, and Table 6 Part III study plan. A complete physical examination including mucocutaneous, lymph nodes, head, neck, chest, abdomen, spine, extremities, and nervous system will be performed at screening. General physical examination, which may include head and neck, chest and abdomen, will be determined by the investigator as clinically indicated. Height and weight were collected only

during the screening examination period. Investigators may perform more frequent tests if clinically indicated.

8.3.4 12-lead ECG

The 12-lead ECG will be measured according to Table 4 Part I study plan, Table 5 Part II study plan, and Table 6 Part III study plan.

A 12-lead ECG will be performed once at screening and once at baseline on D-1. If the 12-lead ECG at screening is performed within 7 days prior to the first dose, 12-lead ECG will not be performed separately at baseline on D-1.

The single-dose PK study of Part I will undergo a single 12-lead ECG 1 hour (\pm 1 hour) before dosing on the day of dosing (D1), the day of leaving the ward (D3), at the safety follow-up visit, and early withdrawal.

A total of 6 12-lead electrocardiograms were required on the day of dosing in the multiple dose escalation PK study of Part II. Serial 12-lead electrocardiograms were performed at 1 hour, 30 minutes, and 15 minutes before dosing on the day of dosing (D1), and at 30 minutes, 1 hour, and 1.5 hours after dosing, with a window of 15 minutes before and after the selected time point. Participants in Part II should remain supine or semi-recumbent for at least 10 minutes prior to each ECG collection. Recordings were performed in triplicate at each time point, at least 1 minute apart, and ECG collection at that time point was completed within 10 minutes. ECG collection for all participants in Part II must be completed prior to PK sampling.

Part III will perform a single 12-lead ECG 1 hour (\pm 1 hour) prior to dosing on the day of dosing (D1, D4, and D7) of each period, on the day of confirming whether to enter the next cycle (D3 and D6), on the day of leaving the ward (D9), and on the day of early withdrawal.

The 12-lead ECG should include heart rate, RR interval, PR interval, QT interval, and calculation of QTcF. Additional ECGs may be performed by the investigator as clinically indicated.

All ECGs are recommended after the participant has rested quietly for at least 5 minutes. Keep supine and awake during ECG collection. A 12-lead electrocardiogram prior to dosing on the day of dosing should be performed prior to PK blood sampling. In studies in Parts I and III, at least 45 minutes apart is required if the test is performed after an invasive test (e.g., PK blood sampling, etc.).

All abnormal ECGs should be identified as clinically significant by the investigator or designee. The number of examinations may be increased for safety purposes. If a clinically significant abnormal ECG is found after enrollment, the investigator will determine whether the participant can continue the study and confirm whether it is recorded as an adverse event based on 8.3.8 Adverse Events.

8.3.5 Blood pregnancy test

For female participants of childbearing potential, blood pregnancy tests will be performed according to Table 4 Part I study plan, Table 5 Part II study plan, and Table 6 Part III study plan (if blood pregnancy test during the screening examination is performed within 2 days prior to the first dose, blood pregnancy test will not be repeated at baseline on D-1). Blood pregnancy tests are not required for women of non-childbearing potential, defined as postmenopausal (\geq 12 months postmenopausal) or documented bilateral tubal ligation, complete oophorectomy, or hysterectomy.

8.3.6 Laboratory tests

For each laboratory test, it should be performed according to Table 4 Part I study plan, Table 5 Part II study plan, and Table 6 Part III study plan and analytical testing should be completed at the study site. Additional laboratory tests may be performed if clinically indicated.

Laboratory Tests

Hematology:	Urinalysis:	Blood chemistry:	Infectious Disease	
Red blood cell count (RBC),	Specific gravity, glucose,	Total bilirubin, direct	Screening:	
hemoglobin (HGB),	protein, ketones, occult	bilirubin, total protein,	Five tests for hepatitis B	
hematocrit (HCT) and total	blood and erythrocytes	albumin, alanine	virus (HBV): hepatitis B	
platelet count (PLT), white		aminotransferase	surface antigen (HBsAg),	
blood cell count (WBC) with		(ALT), aspartate	hepatitis B surface antibody	
differential and proportion		aminotransferase	(HBsAb), hepatitis B e	
(including neutrophil		(AST), alkaline	antigen (HBeAg), hepatitis	
percentage and absolute		phosphatase (ALP),	B e antibody (HBeAb) and	
neutrophil count,		glutamine	hepatitis B core antibody	
lymphocyte percentage and		transpeptidase (GGT),	(HBcAb); treponema	
absolute lymphocyte count,		lactate dehydrogenase,	pallidum antibody, hepatitis	
monocyte percentage and		glucose, urea,	C virus antibody (HCV-	
absolute monocyte count,		creatinine, total	Ab), human	
eosinophil percentage and		cholesterol,	immunodeficiency virus	
absolute eosinophil		triglycerides,	antibody	
percentage, basophil		potassium, sodium,		
percentage and absolute		chloride, calcium,		
basophil percentage and		phosphorus,		
absolute basophil count)		magnesium, carbon		
Coagulation:	Drug abuse screening:	dioxide	Pregnancy test:	
Prothrombin time (PT),	Morphine, ketamine,		Blood pregnancy	
international normalized	methamphetamine,			
ratio (INR), activated partial	dimethyldioxyamphetamine,		Alcohol Screening:	
thromboplastin time	and tetrahydrocannabinol		Alcohol breath test	
(APTT), plasma fibrinogen	acid			
(Fbg), and thrombin time				
(TT)				

8.3.7 Ophthalmic examination

Participants were evaluated ophthalmologically by an ophthalmologist as indicated in Table 4 Part I study plan, Table 5 Part II study plan, and Table 6 Part III study plan. Each ophthalmologic assessment should be performed by the same ophthalmologist whenever possible.

The following assessments will be performed:

- Visual acuity assessments (best corrected), including near and far vision, were performed separately for each eye
- Slit lamp inspection according to local practice
- Intraocular pressure and ophthalmoscopy
- Optical coherence tomography (OCT) of the macular area of both eyes should be performed at each ophthalmic examination and should be performed once in the event of any clinical symptoms or signs suggestive of RPED. Sites should retain duplicate OCT scans. If OCTs are not included in local clinical practice, similar alternative diagnostic methods should be used to screen for RPED
- Add additional tests as clinically indicated as needed

At any other time, participants will undergo a full ophthalmic assessment if abnormal visual symptoms or signs occur.

8.3.8 Adverse Events

An adverse event (AE) is any untoward medical occurrence that occurs in a patient or clinical study participant that is temporally related to the study intervention. It is not necessarily causally related to the study intervention. Adverse events may include, but are not limited to, the following:

- 1) worsening of the original (before entering the clinical trial) medical condition/disease (including symptoms, signs, laboratory abnormalities and/or increased frequency);
- 2) Any new adverse medical condition (including symptoms, signs, newly diagnosed diseases);
- 3) Abnormal and clinically significant laboratory test results (e.g., blood biochemistry, urinalysis) or other tests (e.g., radiological examination, electrocardiogram, vital signs), including those that worsen from baseline and are considered clinically significant according to the investigator's medical and scientific judgment.

The following are not considered adverse events:

Clinically significant laboratory variables or test abnormalities related to the underlying disease are not considered adverse events unless judged by the investigator to be more severe than expected.

Abnormal Laboratory Findings:

Not all abnormal laboratory results were consistent with adverse events. However, abnormal laboratory results must be reported as adverse events if any of the following criteria are met:

- With symptoms;
- Requires clinical intervention or further investigation or additional diagnostic tests;
 - Leading to drug dose modification or discontinuation of study intervention.

If a clinically significant laboratory abnormality is not a sign of a disease or syndrome, the abnormal laboratory test itself should be recorded as an adverse event. If laboratory abnormalities can be described by more precise clinical terms according to standard definitions, clinical terms should be recorded as adverse events.

